Appendix A

Clinic Recruitment Procedures

Recruitment script *“We would like to invite you to participate in a study that is looking at a medication called Gabapentin and how it may affect the pain you experience during your abortion procedure. This medication is very safe and has been used in many other surgical settings however has not been studied in the abortion setting. Your participation is completely voluntary and will not influence the care you receive at the clinic. During this study, you will be given the medication or a placebo, which is a pill that does not contain any medication, 1-2 hours prior to your procedure. Neither you nor the research or clinic staff will know whether you received the Gabapentin or not. We will be looking at your experience during and after the procedure, which will include your experience of discomfort, nausea, vomiting or any side effects. In addition to your visit today, we will contact you tomorrow to briefly ask you some questions. The study procedures today will be completed while you are waiting for your procedure and after your procedure. It should not delay your time at the clinic. You will be reimbursed \$20 for your time today and receive an additional \$10 after completing the phone call tomorrow. If you are interested in participating, we will give you a consent form to read and we can go through the study in detail with you. Again, whether or not you choose to be in the study will not affect your care at the Clinic. Are you interested in seeing if you are eligible?”*

Eligibility checklist:

- 1) What is your age? ____ (must be **18 years-old or older** to be eligible)
- 2) Are you here today for a surgical abortion or medication abortion or another procedure (must be **surgical abortion**)
 - 1) Medical
 - 2) Surgical abortion
 - 3) Other _____
- 3) Are you fluent in English and able to provide informed consent (must be **Yes**)
 - 1) Yes
 - 2) No
- 4) Do you have an allergy, sensitivity or other reason why you can not receive Gabapentin (must be **No**)
 - 1) Yes
 - 2) No
- 5) Do you have any renal disease (must be **No**)
 - 1) Yes
 - 2) No
- 6) Are you currently using gabapentin or pregabalin (must be **No**)
 - 1) Yes
 - 2) No

Duke Consent

You Are Being Asked to Be in a Research Study

What Is a Research Study?

The main purpose of research studies is to gain knowledge. This knowledge may be used to help others. Research studies are not intended to benefit you directly, though some might.

Draft Questionnaire**INTERVIEW DATE** ____ / ____ / ____ **TIME** ____ : ____ **INTERVIEWED BY** ____**Interview Questions:**

1. What is your birthdate? MM/DD/YYYY ____ / ____ / ____
2. Which of the following BEST describes your racial/ethnic background?

 ₁ American Indian/Alaskan Native	 ₅ White/Caucasian
 ₂ Asian	 ₆ Mixed or Multi-racial
 ₃ Black or African American	 ₇ Not Specified/Other
 ₄ Native Hawaiian/Pacific Islander	 ₉ Don't know/refused
3. Do you consider yourself to be Hispanic/Latina/Latino? ₀ NO ₁ YES
4. Is English your first language? ₀ NO ₁ YES
5. What is your marital status?

 ₀ Single/divorced/widowed	 ₂ Cohabitating
 ₁ Married	 ₃ Other
6. What is the highest level of education that you have completed?

 ₁ Less than high-school	 ₄ Associates degree or Technical Certification
 ₂ High-school diploma or GED	 ₅ Bachelors degree
 ₃ Some college	 ₆ Masters degree/Doctoral degree
7. What is your best estimate of the total income of all family members from all sources, before taxes, in [last calendar year in 4 digit format]? by "combined family income," I mean your income PLUS the income of all family members living in this household (including cohabitating partners, and armed forces members living at home).

 ₁ <10,000	 ₅ 75-100,000
 ₂ 10-25,000	 ₆ >100,000
 ₃ 25-50,000	 ₉ Don't know/refused
 ₄ 50-75,000	
8. What is your insurance type

 ₁ medicaid	
 ₂ medicare	
 ₃ private insurance	
 ₄ other, specify _____	
 ₅ uninsured	

Section 2: Substance Use or Medication use

9. Now I will ask you about smoking, alcohol and any substances you may have used.

	a. Ever	b. Past 6 months	c. Frequency of use in past 6 months			d. In the past month , how many per day?
			Daily	Weekly	Monthly	
1. Smoked cigarettes	 ₀ NO  ₁ YES	 ₀ NO  ₁ YES	 ₁	 ₂	 ₃	Cigarettes per day  ₀ Have not smoked in last month  ₁ < 1 ppd  ₂ ≥ 1 ppd
2. Drank alcohol	 ₀ NO  ₁ YES	 ₀ NO  ₁ YES	 ₁	 ₂	 ₃	Drinks per day  ₁ 1 or less  ₂ 2 or more
3. Marijuana	 ₀ NO  ₁ YES	 ₀ NO  ₁ YES	 ₁	 ₂	 ₃	
4. Cocaine/Crack	 ₀ NO  ₁ YES	 ₀ NO  ₁ YES	 ₁	 ₂	 ₃	
5. Heroin	 ₀ NO  ₁ YES	 ₀ NO  ₁ YES	 ₁	 ₂	 ₃	
6. Methamphetamine	 ₀ NO  ₁ YES	 ₀ NO  ₁ YES	 ₁	 ₂	 ₃	
7. Used any other illicit drugs to get high*	 ₀ NO  ₁ YES	 ₀ NO  ₁ YES	 ₁	 ₂	 ₃	
			e. Please list any other drugs used in the past year:			

* This may include hallucinogens (LSD, PCP, mushrooms, peyote), club drugs such as ecstasy, prescription drugs or any other drugs used to get high

10. Do you take any of the following medications?

	a. Ever	b. Past 6 months	c. Frequency of use in past 6 months			
			Daily	Weekly	Monthly	
1. Ibuprofen	 ₀ NO  ₁ YES	 ₀ NO  ₁ YES	 ₁	 ₂	 ₃	
2. Opiate Pain medication (including oxycodone, Percocet, oxycontin)	 ₀ NO  ₁ YES	 ₀ NO  ₁ YES	 ₁	 ₂	 ₃	Type: _____
3. Other pain medication	 ₀ NO  ₁ YES	 ₀ NO  ₁ YES	 ₁	 ₂	 ₃	Type: _____

HEALTH HISTORY

11. Have you ever been pregnant before (prompt: regardless of outcome)?

₀ NO ₁ YES → Answer questions a-e below

- a) How many times? _____
- b) Number of miscarriages or ectopic pregnancies _____
- c) Number of C-sections? _____
- d) Number of vaginal deliveries? _____
- e) Number of abortions? _____ (if 0 → 12)
- f) Number of medical abortions: _____
- g) Number of surgical abortions: _____
- h) Number under local anesthesia: _____

12. Now I will ask you a couple questions about your medical history

Do you have any of the following conditions			Follow-up questions if YES
1	Anxiety	 NO  YES	b. Do you take medication for it?  NO  YES c. Type of medication
2	Depression	 NO  YES	b. Do you take medication for it?  NO  YES c. Type of medication
3	Other psychiatric condition (such as bipolar, schizophrenia, PTSD)	 NO  YES	b. Other condition _____ c. Do you take medication for it?  NO  YES d. Type of medication

13. Have you ever been sexually or physically assaulted?

- NO
- YES, Sexually Assaulted
- YES, Physically Assaulted
- YES, Both sexually and physically assaulted

From Chart Abstraction:

Gestational Age: _____

Height: _____

Weight: _____

Anesthetic Regimen: ₁ LOCAL ₂ IV Moderate Sedation ₃ Deep Sedation

Medications Used:

Time of speculum placement: : AM/PM

Time of speculum removal: : AM/PM

Procedural Complications?

\square_0 NO \square_1 YES: Description:

Preop Assessment

Time: ___ ___ : ___ ___ AM/PM

For these questions we are going to ask you to make a hash mark on a line.

For example, let's say you are asked how much you like Oreo cookies:

How much do you like Oreo cookies? (make a hash mark on the line)

very

You answer the question by making a hash mark on the line according to how much you like or dislike Oreo cookies.

If you liked Oreo cookies a lot, then you might make a hash mark on the line like so:

very
little

very
much

If you liked Oreo cookies more than life itself(!), then you might make a hash mark on the line like so:

very little _____ |

very
much

If you hated Oreo cookies, then you might make a hash mark like so:

very
little

very
much

If you thought Oreo cookies were just "OK," then you might make a hash mark like so:

very
little

very
much

The idea is that if you like Oreo cookies, you make a hash mark on the line closer to the phrase "very much;" the closer you make the hash mark, the more you are saying you like Oreo cookies. If you don't like Oreo cookies, you make a hash mark on the line closer to the phrase "very little;" the closer you make the hash mark, the more you are saying you don't like Oreo cookies.

1. Make a hash mark on the line to indicate how nervous you feel about the surgery you are about to have.

NOT
NERVOUS _____

VERY NERVOUS

2. Make a hash mark on the line to indicate how nervous you feel about the pain you will experience during your procedure.

NOT
NERVOUS _____

VERY
NERVOUS

3. Make a hash mark on the line to indicate how much pain you expect to have during your abortion procedure.

NO
PAIN _____

WORST PAIN
IN MY LIFE

4. Make a hash mark on the line to indicate how much pain you have waiting for your procedure to start.

NO
PAIN _____

WORST PAIN
IN MY LIFE

5. Make a hash mark on the line to indicate how much nausea you currently have

NO
NAUSEA _____

WORST NAUSEA
I HAVE EVER HAD

Have you vomited since you received your study medication?

NO YES

State Trait Anxiety Inventory[1]

Read each statement and select the appropriate response to indicate how you feel right now, that is, at this very moment. There are no right or wrong answers. Do not spend too much time on any one statement but give the answer which seems to describe your present feelings best.

		Not at all	A little	Somewhat	Very much so
1	I feel calm	1	2	3	4
2	I feel secure	1	2	3	4
3	I feel tense	1	2	3	4
4	I feel strained	1	2	3	4
5	I feel at ease	1	2	3	4
6	I feel upset	1	2	3	4
7	I am presently worrying over possible misfortunes				
8	I feel satisfied	1	2	3	4
9	I feel frightened	1	2	3	4
10	I feel uncomfortable	1	2	3	4
11	I feel self confident	1	2	3	4
12	I feel nervous	1	2	3	4
13	I feel jittery	1	2	3	4
14	I feel indecisive	1	2	3	4

15	I am relaxed	1	2	3	4
16	I feel content	1	2	3	4
17	I am worried	1	2	3	4
18	I feel confused	1	2	3	4
19	I feel steady	1	2	3	4
20	I feel pleasant	1	2	3	4

Intraoperative – FOR LOCAL ONLY

1. Make a hash mark on the line to indicate how much pain you had with the speculum insertion.

NO
PAIN _____

WORST PAIN
IN MY LIFE

ACTUAL TIME OF ASSESSMENT _____ : _____

2. Make a hash mark on the line to indicate how much pain you had while the numbing medicine was injected into your cervix.

NO
PAIN _____

WORST PAIN
IN MY LIFE

[Study staff: END OF PCB (Duration since speculum insertion) ____ MINUTES ____ SECONDS]

3. Make a hash mark on the line to indicate how much pain you had while your cervix was opened to prepare for the suction procedure.

NO
PAIN _____

WORST PAIN
IN MY LIFE

[Study staff: END OF CERVICAL DILATION (Duration since speculum insertion) ____ MINUTES ____ SECONDS]

4. Make a hash mark on the line to indicate how much pain you had during the suction procedure.

NO
PAIN _____

WORST PAIN
IN MY LIFE

[Study staff: END OF SUCTION PROCEDURE (Duration since speculum insertion) ____ MINUTES ____ SECONDS]

Immediate Post Op Assessment (on removal of speculum)

Time: ____ : ____ AM/PM

5. Make a hash mark on the line to indicate how much pain you are currently in after removing the speculum.

NO
PAIN _____WORST PAIN
IN MY LIFE**5-Minute Post Op Assessment**

Time: ____ : ____ AM/PM

1. Make a hash mark on the line to indicate the worst pain you have felt up to this point today.

NO
PAIN _____WORST PAIN
IN MY LIFE

2. Make a hash mark on the line to indicate how much pain you are currently in.

NO
PAIN _____WORST PAIN
IN MY LIFE**3.**

Make a hash mark on the line to indicate how much anxiety you are currently experiencing.

NO
ANXIETY _____EXTREMELY
ANXIOUS

4. Make a hash mark on the line to indicate how much nausea you are currently experiencing.

NO
NAUSEA _____WORST NAUSEA
I HAVE EVER HAD

5. Have you vomited since you had your procedure?

 ₀ NO ₁ YES

10-Minute Post Op Assessment

Time: ____ : ____ AM/PM

1. Make a hash mark on the line to indicate the worst pain you have felt up to this point today.NO
PAIN _____WORST PAIN
IN MY LIFE**2. Make a hash mark on the line to indicate how much pain you are currently in.**NO
PAIN _____WORST PAIN
IN MY LIFE**3. Make a hash mark on the line to indicate how much anxiety you are currently experiencing.**NO
ANXIETY _____EXTREMELY
ANXIOUS**4. Make a hash mark on the line to indicate how much nausea you are currently experiencing.**NO
NAUSEA _____WORST NAUSEA
I HAVE EVER HAD5. Have you vomited since you had your procedure? ₀ NO ₁ YES

SIDE EFFECTS: Do you have any of the following?

Dizziness	 ₀ NO  ₁ YES, mild  ₂ YES, moderate  ₃ YES, severe
Ataxia (lack of muscle control)	 ₀ NO  ₁ YES, mild  ₂ YES, moderate  ₃ YES, severe
Somnolence (sleepiness or drowsiness)	 ₀ NO  ₁ YES, mild  ₂ YES, moderate  ₃ YES, severe
Asthenia (weakness, lack of energy)	 ₀ NO  ₁ YES, mild  ₂ YES, moderate  ₃ YES, severe
Headache	 ₀ NO  ₁ YES, mild  ₂ YES, moderate  ₃ YES, severe
Amblyopia (vision in one eye reduced/lazy eye)	 ₀ NO  ₁ YES, mild  ₂ YES, moderate  ₃ YES, severe

Post- anesthetic alдрete recovery score : modified Criteria	Points
Oxygenation	
SpO ₂ > 92% on room air	2
SpO ₂ > 90% on oxygen	1
SpO ₂ < 90% on oxygen	0
Respiration	
Breathes deeply and coughs freely	2
Dyspneic, shallow or limited breathing	1
Apnea	0
Circulation	
BP +/- 20% of normal	2
BP +/- 20-50% of normal	1
BP > 50% of normal	0
Consciousness	
Fully awake	2
Arousable on calling	1
Not responsive	0
Activity	
Moves all extremities	2
Moves two extremities	1
No movement	0

30-Minute Post Op Assessment

Time: ____ : ____ AM/PM

1. Make a hash mark on the line to indicate the worst pain you have felt up to this point today.NO
PAIN _____WORST PAIN
IN MY LIFE**2. Make a hash mark on the line to indicate how much pain you are currently in.**NO
PAIN _____WORST PAIN
IN MY LIFE**3. Make a hash mark on the line to indicate how much anxiety you are currently experiencing.**NO
ANXIETY _____EXTREMELY
ANXIOUS**4. Make a hash mark on the line to indicate how much nausea you are currently experiencing.**NO
NAUSEA _____WORST NAUSEA
I HAVE EVER HAD

4. Have you vomited since you had your procedure?

 ₀ NO ₁ YES

Discharge Assessment

Time: ____ : ____ AM/PM

1. Make a hash mark on the line to indicate the worst pain you have felt up to this point today.

NO
PAIN _____

WORST PAIN
IN MY LIFE

2. Make a hash mark on the line to indicate how much pain you are currently in.

NO
PAIN _____

WORST PAIN
IN MY LIFE

3. Make a hash mark on the line to indicate how much anxiety you are currently experiencing.

NO
ANXIETY _____

EXTREMELY
ANXIOUS

4. Make a hash mark on the line to indicate how much nausea you are currently experiencing.

NO
NAUSEA _____

WORST NAUSEA
I HAVE EVER HAD

5. Have you vomited since you had your procedure? ₀ NO ₁ YES

Post- anesthetic Aldrete recovery score Modified Criteria [2]	Points
Oxygenation SpO ₂ > 92% on room air SpO ₂ > 90% on oxygen SpO ₂ < 90% on oxygen	2 1 0
Respiration Breathes deeply and coughs freely Dyspneic, shallow or limited breathing Apnea	2 1 0
Circulation BP +/- 20% of normal BP +/- 20-50% of normal BP > 50% of normal	2 1 0
Consciousness Fully awake Arousable on calling Not responsive	2 1 0
Activity Moves all extremities Moves two extremities No movement	2 1 0

24 hours post-procedure measures

Time: _____ AM/PM

Did you fill any pain medication prescription? ₀ NO ₁ YES

Have you taken any medication since you left the clinic for pain, nausea, vomiting or any other medication

Have you vomited since you left the clinic? NO YES, number of times _____

Overall satisfaction with experience 0-10 scale (0 = very dissatisfied; 10 = very satisfied): _____

Quality of Recovery Survey[3]

Part A

	How have you been feeling in the last 24 hours? (0 to 10, where 0 = none of the time [poor] and 10 = all of the time [excellent])	0-10
1	Able to breathe easily	
2	Been able to enjoy food	
3	Feeling rested	
4	Have had a good sleep	
5	Able to look after personal toilet and hygiene unaided	
6	Able to communicate with family and friends	
7	Getting support from hospital doctors and nurses	
8	Able to return to work or usual home activities	
9	Feeling comfortable and in control	
10	Having a feeling of general well-being	

Part B

	Have you had any of the following in the last 24 hours? (0 to 10, where 10= none of the time [excellent] and 0 = all of the time [poor])	0-10
1	Moderate pain	
2	Severe pain	
3	Nausea or vomiting	

4	Feeling worried or anxious	
5	Feeling sad or depressed	

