- To evaluate side effects or adverse events of gabapentin in this setting
- To identify subgroups where adjunctive gabapentin may be more effective at reducing perioperative pain such as gestational age ranges and patient characteristics (age, gravidity, substance abuse, preoperative anxiety level).

Background and Rationale:

Surgical abortions in North America are typically performed using either local anesthetic with oral analgesics or moderate sedation. A 2009 Cochrane review of evidence for pain control assessed that paracervical block in reducing abortion related pain is limited, while the addition of ibuprofen and naproxen can slightly reduce intraoperative and post operative pain [6]. Evidence supports the benefit of conscious sedation at reducing intraoperative and post-operative pain in abortions [7]. General anesthesia can be useful in some settings, however its use is limited due to cost, staffing and potential for additional risks. Further, studies have found, although better at reducing pain during the procedure, general anesthesia is not superior to moderate sedation for post-operative pain [8]. Other recently examined adjuncts to pain control have not proven to be beneficial in this setting [9-11].

Gabapentin is widely used to treat neuropathic and chronic pain. Mechanism of action may include calcium channel blockade and modulation of nociceptive neurotransmitters. Clinical trials support use of perioperative pregabalin and gabapentin to reduce perioperative and post-operative pain in a variety of clinical settings, for both major and minor surgical procedures [2, 12]. While pregabalin has a faster peak plasma concentration, gabapentin is a less expensive option with peak concentrations reached by 2 hours, with substantial evidence to support routine use and safety in reducing perioperative pain. In a systematic review of 22 randomized controlled trials (RCT), a single preoperative dose of gabapentin significantly reduced 24-hour

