Women undergoing a procedure who meet study inclusion criteria and complete informed consent will be eligible for participation. *Randomization* will be done using computer-generated random numbers (randomization.com) in variable blocks of 8 and 10. *Allocation* concealment will be maintained by identically labeled sealed sequentially numbered opaque pill containers. Gabapentin and placebo tablets will be indistinguishable by appearance, thus maintaining blinding for participants and assessors. To maintain double *blinding* for both investigators and participants, an individual not associated with study conduct will create the randomization sequence and allocation containers. The randomization assignments will only be revealed at the point of data analysis or if an interim assessment is needed.

Enrollment:

After the final perioperative clearance, the individual will be randomized and receive their method allocated by the clinic nurse. The study staff will review the enrollment questionnaire that includes demographic questions. Following completion of the questionnaire, the participant will wait before moving to our procedure room (this will occur approximately 1-2 hour after nursing review and receipt of the study intervention). Prior to initiating the procedure, study staff will administer the preoperative questions. The physician will then complete the uterine aspiration while the study staff remains outside of the operative room. Immediately following the procedure, the study staff will then administer the immediate post-operative questions and follow the participant to the recovery room to complete the remaining questions assessed at 5 minutes, 10 minutes, 30 minutes and at discharge. When the discharge questions are complete, the

participant will receive a \$20 gift card and instructed to expect a follow-up call the following day.

Follow-up:

On the day following the procedure (approximately 24 hours after the procedure), study staff will call the participant to complete the follow-up questions. On completion of the questions, an additional \$10 will be transferred to the gift card.

Withdrawals, losses and deviations:

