Randomization to study method will occur after completion of all intake forms and consent, immediately before the pill is to be taken, thus reducing the possibility of withdrawal after randomization. Primary outcome measures and most secondary outcome measures will be assessed immediately before, during or after the abortion procedure, thus any loss to follow-up will be limited to those who consent to, but change their mind while waiting for their procedure. Based on current clinical practice at this clinic, withdrawal after consent is extremely rare. Our secondary outcomes assessed post-operatively after discharge will be collected via the phone. We will maximize completion of these assessments through the following steps: participants will be told beforehand about the telephone contact following the procedure, a cellular telephone number will be collected and tested at the clinic, a secondary phone number and email will be collected as a backup, participants will be given a contact number for the study coordinator should they have any challenges with receiving a phone calls, and participants will receive an additional \$10 sent to their gift-card following the completion of their phone assessment.

Data Collection/Outcome measurements:

Outcome measures and baseline variables are described in Table 1.

Primary study outcome

Our primary outcome measure will be pain score using an 100-mm visual analog scale (VAS) measured 5 minutes after removal of the speculum.

Secondary Outcomes:

We will also be measuring pain on the 100-mm VAS preoperatively immediately prior to the procedure, after the procedure, 10 minutes and 30 minutes following the procedure and at discharge. Nausea, using a VAS, and vomiting will be assessed preoperatively immediately prior to the procedure and post operatively at 10 minutes, 30 minutes and at discharge. Anxiety prior to the procedure will be measured using the preoperative state trait anxiety inventory. Side effects will be assessed using a checklist prior to discharge. We will also be contacting participants on post-operative day 1 to assess pain, nausea, vomiting, side effects and general satisfaction with the procedure (on a 5-point scale). The quantity and type of medications used perioperatively and post-operatively including medications used at home in the 24 hours post-operatively will be abstracted from the clinical record and assessed on the phone.

Baseline Characteristics and covariates:

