We will collect baseline demographics, medical history (gravidity, parity, prior abortions (medical and surgical), gestational age, drug and alcohol use, psychiatric or sexual assault history), medications used at home and given at the clinic preoperatively, indication for procedure (personal/social, fetal or maternal health)).

Study Size and Power:

We will enroll a total of 96 women. Assuming a standard deviation of 26 mm on the 100-mm visual analog scale (VAS), based on prior studies, this will provide us with an 80% power, using a p-value of 0.05, to detect a 15 point difference in pain among all participants. A difference of 15-20 mm has been assessed to be clinically meaningful in prior studies. Given that our primary outcome will be measured immediately after the procedure, our loss to follow-up will be minimal. A 100-mm pain visual analog scale has been shown to be useful for the evaluation of pain in prior pain abortion research [5, 6] with a mean standard deviation in previous studies of approximately 26 mm [5]. We are assuming no loss-to-follow-up as our primary outcome will be measured at the time of the procedure.

Data Management and Analysis

Data Management:

Prior to study initiation, a database will be developed using a web-based password-protected relational database (REDCap). All data will be collected will be recorded on clinical research forms (CRFs) and entered into the database at the end of each day. All CRF source documents will be filed and stored for future reference. See monitoring and oversight section below for further details on procedures and protections.

Analytic Plan:

We will compare groups on the primary continuous outcome measure (pain score on 11-point VAS) using T-tests. Chi-square and T-tests will be used to evaluate secondary outcomes for categorical and continuous variables, respectively. Baseline characteristics will be evaluated for potential interaction or confounding with primary and secondary outcomes.

Upon study completion at each site for the prospective meta-analysis, data from each site will contribute to the final meta-analysis using criteria outlined in the Cochrane Handbook for Systematic Reviews of Interventions. Site RCT publications will mention contribution to this PMA. Subgroup analyses will address gabapentin adjunct to local anesthesia and moderate sedation, as well as by specified population characteristics and gestational age.

Ethical Concerns

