An adverse event (AE) is defined as any health-related reaction, effect, toxicity or abnormal laboratory result that a study participant experiences during the course of the study, irrespective of relationship to the study intervention. This includes changes in a participant's condition that have or could have a deleterious effect on a participant's health or well-being. A serious adverse event (SAE) is defined as any experience that is fatal or life-threatening, requires

in-patient hospitalization or prolongation of an existing hospitalization, or results in a persistent or significant disability or incapacity.

This study uses an additional medication for pain control in the setting of outpatient abortion. These activities are not anticipated to be associated with any deleterious impact on participants' health or well-being beyond the risks associated with the abortion procedure. AEs will be managed according to good clinical practice and the judgment of the on-site physician. All clinical and laboratory AEs will be followed-up closely by study staff. Any SAEs will be expeditiously reported to the principal investigators, via a designated SAE form. Notification and submission of SAE forms should occur within 48 hours of the site awareness of the SAE. The PI will then make the final independent judgment as to the severity, relatedness, and anticipated or unanticipated nature of the SAE and finalize the Human Subjects Adverse Event Report Form. If the event is determined to be serious, unanticipated, and the relationship is anything other than probably or definitely not related, then the PI will report the event within 48 hours and submit the required forms to the IRB at Duke. Thus, all anticipated SAEs that are at least possibly related to study intervention and all deaths that are at least possibly related to study intervention will be submitted to the Duke IRB.

The study may be discontinued at any time by an IRB at a participating institution or the Office for Human Research Protection. We will additionally have a medical monitor to review any adverse event and periodically review side effects to see if there are an increased number of events than anticipated by routine clinical care. If any suspicion for increased risk exists, study allocation may be revealed for a preliminary analysis and if related to the study intervention, the study could be prematurely ended.

Data Monitoring Committee/Study Termination

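### The side-effect checklist does not separate new symptoms from standing ones, which raises crude rates in both arms and pulls their difference toward zero; its vision item has the same gap and can miss change in both eyes

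*Combined protocol and SAP*

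**What the plan says.** Side effects are a named secondary aim: "To evaluate side effects or adverse events of gabapentin in this setting". The Secondary Outcomes paragraph says "Side effects will be assessed using a checklist prior to discharge", and the opening hypotheses expect few adverse effects.

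The instrument is in the Draft Questionnaire, under the 10-Minute Post Op Assessment. The stem is "SIDE EFFECTS: Do you have any of the following", followed by dizziness, ataxia, somnolence, asthenia, headache and a vision item, each graded none, mild, moderate or severe. The vision item reads "Amblyopia (vision in one eye reduced/lazy eye" (closing bracket omitted here).

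Other items on the form do carry a time anchor. The preoperative assessment asks "Have you vomited since you received your study medication", and later vomiting items are tied to the procedure or to leaving the clinic.

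The Analytic Plan states: "Chi-square and T-tests will be used to evaluate secondary outcomes for categorical and continuous variables, respectively". The comparison is with placebo: "Gabapentin and placebo tablets will be indistinguishable by appearance, thus maintaining blinding for participants and assessors". The Adverse events section defines an event as something a participant "experiences during the course of the study, irrespective of relationship to the study intervention".

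**The concern.** A woman who arrives with a headache, low energy or dizziness will truthfully tick the item whichever pill she received. Nothing collected earlier allows that to be subtracted. The Health History covers pregnancy, psychiatric conditions and assault. The preoperative form covers nervousness, pain, nausea, vomiting and anxiety, and is itself completed after the pill. The 24-hour form does not repeat the six items.

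The result is a harm comparison biased toward no difference, in a trial that hypothesises few adverse effects. The crude counts are affected too. The Adverse events section has a medical monitor review side effects against what routine care would produce, and counts that mix old and new symptoms are a weak basis for that.

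The vision item has a second problem. Its gloss describes a condition of one eye that may be lifelong. A woman with a long-standing lazy eye can truthfully say yes, and a woman whose sight has blurred in both eyes since the pill can truthfully say no. Placebo control cannot recover events that the item does not capture.

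**Working it through.** **The plan's own figure.** Study Size and Power gives SD 26 mm, difference 15 mm, 80% power and significance level 0.05 (sidedness not stated). Two-sided, n per arm = 2 × (1.960 + 0.842)² × 26² / 15² = 47.2, rounded up to 48, so 96 in total. The stated size reproduces. It concerns pain only; the plan gives no power or expected rate for any side effect.

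**Inputs for this check.**
- 48 per arm: 96 women with equal allocation (Recruitment; Study Size and Power).
- Test: two-sided chi-square without continuity correction, significance level 0.05. The plan names chi-square; the other details are assumed.
- New-symptom rates p and standing prevalence b: assumed, because the documents give neither. Three pairs of rates are shown.

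**Model.** With b equal in the two arms by randomization, and standing symptoms still present at the check:

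- observed rate = b + (1-b) × p
- difference = [b + (1-b)p_G] − [b + (1-b)p_P] = (1-b)(p_G − p_P)

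(G = gabapentin, P = placebo.) If p_G = p_P the difference is 0 for every b. For example, p = 10% in both arms and b = 30% gives 0.30 + 0.70 × 0.10 = 37% in each.

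**Results**, with power found by summing the binomial probabilities of all outcomes that reject:

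| New-symptom rates, placebo vs gabapentin | b | Observed rates | Difference (points) | Power |
|---|---|---|---|---|
| 5% vs 20% | 0 | 5.0% vs 20.0% | 15.0 | 66% |
| | 10% | 14.5% vs 28.0% | 13.5 | 37% |
| | 20% | 24.0% vs 36.0% | 12.0 | 26% |
| | 30% | 33.5% vs 44.0% | 10.5 | 18% |
| 10% vs 35% | 0 | 10.0% vs 35.0% | 25.0 | 86% |
| | 10% | 19.0% vs 41.5% | 22.5 | 69% |
| | 20% | 28.0% vs 48.0% | 20.0 | 53% |
| | 30% | 37.0% vs 54.5% | 17.5 | 41% |
| 20% vs 50% | 0 | 20.0% vs 50.0% | 30.0 | 88.5% |
| | 10% | 28.0% vs 55.0% | 27.0 | 78% |
| | 20% | 36.0% vs 60.0% | 24.0 | 67% |
| | 30% | 44.0% vs 65.0% | 21.0 | 55% |

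Power falls faster than the difference because the variance also grows. For 5% vs 20% the pooled rate moves from 12.5% to 38.75%, so p(1-p) rises from 0.109 to 0.237.

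For a symptom that is rare at baseline the loss is much smaller. At b = 2%, the 5% vs 20% case falls from 66% to 58%.

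**Vision item.** No calculation is offered, because the documents give no prevalence of lazy eye. The argument is from the wording alone: one eye only, and no onset.

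**The case against.** The strongest reply is that the trial is randomized, blinded and placebo-controlled. A reader might infer from the form that standing symptoms will be counted as effects of gabapentin. The documents do not support that. No rule attributes a ticked item to the drug, adverse events are recorded regardless of cause, and the planned comparison is between arms. With no drug effect the expected difference is zero at any b. This reply stands; dilution and inflated crude rates remain.

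Second, the size rests on assumptions, and 5% vs 20% is a sensitive choice, with only 66% power even under perfect wording. Baselines of 10% to 30% may suit tiredness or headache, but nothing supports them for ataxia or vision. The calculation also reduces four grades to yes or no, although worsening could show as a higher grade. This stands too, which is why a range is given.

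Third, a reader might infer that the vision item cannot pick up any new change in sight. That goes too far. New reduced vision in one eye fits the gloss, trained staff administer the questions, and the adverse event definition covers changes in condition, so a reported change has another route. The item also mirrors amblyopia in the protocol's own list of gabapentin effects. The narrower fault remains.

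Finally, this is a form labelled draft, for a secondary outcome that was never powered. That limits the importance of the point but does not answer it.

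**Conclusion.** The point holds as a measurement weakness in a secondary outcome. As written, the checklist mixes standing and new symptoms, and no pre-dose record allows them to be separated afterwards. The expected difference shrinks to (1-b) of its true size. That follows from the wording and from randomization, given that standing symptoms persist to the check. The loss of power depends on assumed rates: from slight, where a symptom is rare at baseline, to a fall from 66% to 18% in the least favourable case shown.

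The bias is toward missing a harm, not toward inventing one. Gabapentin-arm rates would overstate drug effects only if read without the placebo arm. The vision item cannot distinguish new from old one-eye loss and can miss change in both eyes. The primary pain analysis is untouched.

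**What to change.** Reword two lines of the draft form:

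- Stem: *Do you now have any of the following that is new or worse than before you took the study pill?* Keep the four severity grades.
- Vision line: *Blurred, double or otherwise changed vision.*

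Asking about symptoms present now keeps the existing window. A stem asking about anything experienced since the pill would widen the recall period and change the outcome.

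Alternatively, give the same checklist (with the revised vision line) once before the pill and count only new or worse grades. Its place would need stating: the Enrollment section has the questionnaire reviewed after the pill is received, whereas the section on withdrawals puts all intake forms before randomization.

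Cost: under the first option women judge onset shortly after a procedure under oral sedation; under the second they answer six more questions before dosing. The other sites in the prospective meta-analysis should use the same wording, so that side-effect rates can be pooled. The change must come before data collection, because onset cannot be recovered from answers already given.
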